7.3. INTERVENTION

Subjects will follow their assigned condition for 6 weeks. Subjects in the control group will be monitored by study staff but otherwise uninstructed in regard to activity and nutrition. Their adherence to the provided educational materials is entirely up to them. The experimental group will be initiated into a 4-6-week (28-42 days depending on subject availability for the last testing day) progressive protocol on the Pro2col app. They will receive daily updates, notification, and education regarding healthy habits such as exercise, hydration, and improved nutrition practices. An AI coach will be responsible for providing instructions and feedback to all application users.

7.4. **POST-TESTING**

Subjects who complete the 4-6-week (28-42 days depending on subject availability for last testing day) intervention and continue to be eligible for this study will then complete post testing. Subjective questionnaires will be provided to assess items such as current activity levels, nutrition habits, and lifestyle factors related to health and wellness. Enrolled and randomized subjects will also receive a blood pressure cuff and digital scale to record blood pressure and bodyweight/body composition, respectively. Moreover, subjects will complete electronic calculations to estimate their healthspan and biological age. Finally, subjects will perform three physical fitness tests, including:

- Timed one mile walk/run
- Push-ups (or modified push-ups for women) to exhaustion
- Chair get-ups to exhaustion

Finally, upon completion of the study (or early withdrawal), subjects will be directed to delete the investigational application from their smart device, and no further data will be collected.

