7.5. Subject Withdrawal and Early Termination

Subjects may withdraw from the study at any time at their own request, or they may be withdrawn at any time at the discretion of the investigator or Sponsor for safety, behavioral, or administrative reasons. Every effort should be made to document the subject outcome, if possible. The investigator should inquire about the reason for withdrawal, request the subject return for a final visit, and if applicable, follow-up with the subject regarding any unresolved adverse events.

If the subject withdraws from the study and also withdraws consent for disclosure of future information, no further evaluations will be performed, and no additional data will be collected. The Sponsor may retain and continue to use any data collected before such withdrawal of consent.

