10.3. Analyses

10.3.1 Primary Analysis

Descriptive statistics will be reported including mean, median, minimum and maximum values, standard deviation, and 95% confidence intervals of the mean. All outcome measure data will be reported as mean \pm standard deviation (SD). Relative and absolute changes between groups for all outcomes will be reported and analyzed for statistical significance using paired *t* tests. Additionally, effect sizes will be calculated as Cohen's d_g

for between-subjects analyses as the difference between group means divided by the pooled standard deviation times a correction factor [1]. Statistical significance will be set at p < 0.05 and all analyses will be performed using SPSS Version 28.0.

Cohen's
$$d_g = \frac{\left(X_{Group A} - X_{Group B}\right)}{SD_{pooled}} \times \left(1 - \frac{3}{4 \times (N1 + N2) - 9}\right)$$

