10.3.3 Safety Analysis

All safety analyses and summaries will be based on the Safety population. The number and percentage of subjects reporting AEs during the study will be tabulated and summarized. Subjects experiencing serious adverse events, treatment-related adverse events, and discontinuation from the study due to adverse events will also be summarized. Treatment-related adverse events will include events marked as being at least possibly or probably related to the study dose. Adverse events will be presented by severity and by relation to treatment. Enrollment status with respect to number of subjects enrolled, completed, lost-to-follow and discontinuation regardless of reason will be presented. All adverse events and concomitant medications will be presented in listings.

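### Non-completers have no assigned outcome tests and no efficacy set is named, so the plan as written compares completers; intervention length and post-test timing also conflict

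*Combined protocol and SAP*

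**What the plan says.** **Who is post-tested.** Section 7.4 gives post-testing to "Subjects who complete the 4-6-week (28-42 days depending on subject availability for last testing day) intervention and continue to be eligible for this study". It adds that, at completion or early withdrawal, "subjects will be directed to delete the investigational application from their smart device, and no further data will be collected".

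**What happens on withdrawal.** Section 7.5 allows withdrawal at the subject's request or "at the discretion of the investigator or Sponsor for safety, behavioral, or administrative reasons". It says "Every effort should be made to document the subject outcome, if possible" and tells the investigator to "request the subject return for a final visit". It ends evaluations only for a subject who "also withdraws consent for disclosure of future information, no further evaluations will be performed". It does not say what is measured at the final visit.

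**Who is analysed.** Section 10.3.1 says only: "Relative and absolute changes between groups for all outcomes will be reported and analyzed for statistical significance". No efficacy set is named and no rule covers a missing post-test. For safety, 10.3.3 says "All safety analyses and summaries will be based on the Safety population", a population that is not defined. Per Protocol Population appears in the abbreviation list and nowhere else. Section 7.6.2 defines Completed and Discontinued/Withdrawal as statuses but ties neither to an analysis.

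**Length and timing.** Sections 3.1, 6.2, 7.3 and 7.4 give 28-42 days, depending on when the subject is available for the last test. Section 7.3 also says that subjects follow their condition for 6 weeks, and 5.1 sets weeks 1-6 as the intervention. Post-testing is at week 7 in Section 4 and in weeks 7-8 in 5.1.

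**The concern.** A subject who stops the intervention but does not withdraw consent has no assigned outcome tests. 7.4 excludes that subject from post-testing, and 7.5 requests a visit with no content. With no analysis set stated, the data that exist at the end will in practice be those of completers.

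That group is formed after randomisation. The trial is unblinded (6.4). One arm follows a programme of fasting windows, diet, step goals and logging; the other receives printed guidance. Staff who know the assignment may also withdraw subjects for behavioural or administrative reasons. Unequal and outcome-related loss is therefore plausible. If poor responders leave the app arm more often than the control arm, the comparison flatters the app; the opposite pattern would understate it.

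The timing conflict adds a second problem. If availability sets the last test day, the treatment effect has no single time point and exposure varies between subjects. Section 7.3 attaches 4-6 weeks to the experimental arm only, while 7.4 applies it to subjects generally, so the text does not settle whether both arms share one test schedule.

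**Working it through.** **1. The withdrawal passages side by side.** Take a subject who stops in week 3 and keeps consent. Under 7.4 there is no post-test, the app is deleted and data collection ends. Under 7.5 the outcome is to be documented if possible and a final visit requested, with evaluations still allowed. If the final visit comes first and app deletion second, both can be followed. Neither section then assigns that subject an outcome test, so the post-test value is missing.

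**2. The plan's own figure, as input.** Section 10.1 gives 50 subjects for an effect size of 0.8. Power, sidedness and allocation are not stated; I assume 80%, two-sided 0.05 and 1:1.

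- n per arm = 2(1.960 + 0.842)² / 0.8² = 24.5, so 25 per arm and 50 in total. The figure reproduces.
- Section 5.1 accepts a minimum of 20 completers per group. Against 25 per arm that is 5 lost, or 5/25 = 20%.
- Power at 0.8 by the noncentral t is 79% with 25 per arm and 69% with 20, so 50 contains no allowance for loss.

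**3. Size of selective loss (illustration; the dropout pattern is assumed).** Change has SD 1 and there is no true effect. Control loss is random. In the app arm, the 5 subjects with the lowest value of a staying tendency are lost, and that tendency correlates r with change. The test is a two-sample t test on change; 10.3.1 says paired, but the arms are independent and that is a separate matter. There were 100,000 replicates.

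Expected bias = r × (mean of the top 20 of 25 standard normal values) = r × 0.3362:

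- r = 0.3: 0.101
- r = 0.5: 0.168
- r = 0.7: 0.235

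The large-sample form r × φ(z)/(1 − p) with p = 0.20 gives 0.105, 0.175 and 0.245. Simulated values, with two other loss rates for range:

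| Lost per arm | r = 0.3 | r = 0.5 | r = 0.7 |
|---|---|---|---|
| 3 (12%) | 0.07 SD, 6% | 0.11 SD, 7% | 0.15 SD, 9% |
| 5 (20%) | 0.10 SD, 6% | 0.17 SD, 9% | 0.23 SD, 13% |
| 10 (40%) | 0.19 SD, 8% | 0.31 SD, 14% | 0.44 SD, 25% |

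Percentages are false positives at a nominal 5%. With selective loss in the control arm only, the sign reverses. With equal selective loss in both arms, the bias is zero.

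**4. Timing.** Six weeks is 6 × 7 = 42 days, so week 7 starts on day 43. A subject whose intervention ends on day 28 finishes 43 − 28 = 15 days before that. Only the 42-day length runs straight into a week 7 post-test. Week 7 and weeks 7-8 are compatible with each other; 28-42 days is not compatible with a fixed 6 weeks. Within 6.2, steps build over 4-6 weeks while water and the eating window build over 6.

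**The case against.** **A flat contradiction between 7.4 and 7.5.** A reader might infer this, but the text does not force it. The sentence in 7.4 covers completion as well as withdrawal and is tied to deleting the app, so it can describe the last step after the final visit. The instruction in 7.5 to document the outcome also counts for something. What stands is narrower: that instruction names no outcome, test or time.

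**Exclusion on the baseline PHQ-9 after randomisation.** The loose ordering in 7.1 and 7.2, where condition assignment and randomised subjects are mentioned before or during baseline testing, invites this reading. The other sections point against it. 5.1 randomises after baseline testing, 5.2.2 makes the PHQ-9 score an exclusion criterion, 6.1 assigns only subjects who meet all entry criteria, and 7.6.1 defines Enrolled the same way. Only the wording of 7.1 and 7.2 needs aligning.

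**A day-28 subject left part-way up the step ladder.** The six-week list in 6.2 suggests this, but it is labelled an example, and the same section says the step target is reached over 4-6 weeks. A shortfall in step goals cannot be computed from it. Such goals are in any case not achieved steps and should not be set against the improvement cited in 10.1.

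**Pilot status and planned disposition.** The trial is exploratory, and 10.3.3 already reports numbers completed, lost and discontinued. Both are fair points. But 10.3.1 still tests for significance at 0.05, and disposition counts do not say who enters the efficacy comparison.

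**Conclusion.** The point holds in this form. Non-completers have no assigned outcome tests, no efficacy set or missing-data rule is stated, and the plan followed as written compares completers. At the 20% loss implied by the plan's own minimums, one-sided selective loss of moderate strength gives 0.10 to 0.23 SD of bias and 6% to 13% false positives.

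Those figures rest on an assumed dropout pattern, 1:1 allocation and a two-sample test. They show what the plan leaves open and do not forecast the result. A reader might infer that the trial will favour the app; the documents give no basis for a direction.

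The conflict between 28-42 days, 6 weeks and week 7 is an inconsistency in the text and needs no assumption. That the arms will be tested on different days is only a possibility: 7.3 allows it, while 7.4 and 5.1 speak of subjects or both groups. This should be corrected, and most of it can be done by amending text.

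**What to change.** 1. **Sections 7.4 and 7.5.** Ask every randomised subject for post-test outcomes in one window common to both arms, whether or not the intervention was completed, unless consent for data collection is withdrawn. Collect them before the app is deleted or by another remote route, for example an emailed questionnaire, or scale, blood pressure and step readings sent by the subject. Whether a withdrawn or no-longer-eligible subject does the physical tests stays with the investigator's safety judgement.
2. **Section 10.3.1.** Analyse all randomised subjects as assigned, with completers as a sensitivity analysis, and state how a missing post-test is handled. Add to the disposition already planned in 10.3.3 the number not post-tested for each outcome and the actual test day, both by arm.
3. **Timing and order.** Reconcile intervention length and post-test timing across 3.1, Section 4, 5.1, 6.2, 7.3 and 7.4. Align the order of randomisation and baseline testing in 7.1 and 7.2 with 5.1 and 6.1. No length is proposed here; the passages must agree.

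**Cost.** This takes more than wording. Under Section 4 and Appendix 1, several questionnaires, blood pressure entry and step transfer run through the app, so the app must be deleted later or a second collection route set up. Non-completers need reminders, although those already enrolled will have been sent the scale and cuff. Scheduling becomes less flexible and the effect estimate may be diluted. Some app-based scores will still be missing, since Appendix 1 ties healthspan and biological age to the physical tests.

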7.5. Subject Withdrawal and Early Termination

Subjects may withdraw from the study at any time at their own request, or they may be withdrawn at any time at the discretion of the investigator or Sponsor for safety, behavioral, or administrative reasons. Every effort should be made to document the subject outcome, if possible. The investigator should inquire about the reason for withdrawal, request the subject return for a final visit, and if applicable, follow-up with the subject regarding any unresolved adverse events.

If the subject withdraws from the study and also withdraws consent for disclosure of future information, no further evaluations will be performed, and no additional data will be collected. The Sponsor may retain and continue to use any data collected before such withdrawal of consent.

7.6.1. Protocol Deviations

Protocol deviations will be tracked and managed during the conduct of the study. A protocol deviation is defined as a non-conformance from the protocol which occurs at any time during the conduct of the study. Exceptions will not be granted by the Sponsor for any planned or unplanned deviation. All protocol deviations will be tracked.

| Classification | Criteria |
|----------------|---|
| Screen Failure | Signs the ICD but does not meet entry criteria or withdraws prior to Baseline Testing |
| Enrolled | Signs the ICD and met all inclusion/exclusion criteria |
| Initiated | Signs the ICD and successfully completes Baseline Testing |

7.6.2 Status Classification

| Discontinued/Withdrawal | Signed | the l | ICD bi | it does | s not successfu | ally complet | e the | Intervention | |
|-------------------------|--------|--------|--------|---------|-----------------|--------------|-------|--------------|-----|
| Completed | Signs | the | ICD | and | successfully | completes | the | Intervention | and |
| | Post-T | esting | g | | | _ | | | |

8. ASSESSMENTS

8.1. Clinical Evaluations

The following clinical evaluations will be conducted during the study review:

- Medical and Medication History An assessment of the subject's health status prior to enrollment to ascertain appropriateness for study participation based on inclusion/exclusion criteria.
- Adverse Event Reporting Investigator examination of the subject and notation of any observations made by the study investigator of a potential adverse event.

8.2. Assessment of Safety

Self-reported and observed adverse events.

9. ADVERSE EVENT REPORTING

9.1. Introduction

All observed or volunteered adverse events regardless of treatment group or suspected causal relationship to the INP(s) will be reported as described in the following sections.

For all adverse events, the investigator must pursue and obtain information adequate both to determine the outcome of the adverse event and to assess whether it meets the criteria for classification as a serious adverse event requiring immediate notification to the Sponsor or its designated representative. For all adverse events, sufficient information should be obtained by the investigator to try to determine the causality of the event. For adverse events with a suspected causal relationship to the experimental product, follow-up by the investigator is required until the event or its sequel resolve or stabilize at a level acceptable to the investigator, and Sponsor concurs with that assessment.

9.2. Reporting Period

Serious adverse events require immediate notification within **24 hours** to the IRB and its designated project manager. When reporting a serious adverse event, the investigator or designee completes the SAE form with as much information as possible however, at a minimum the Subject ID, Name of INP, SAE, and Name of person reporting the event.

All adverse events (serious and non-serious) must be collected on the subject's case report form (CRF) from the time the subject signed informed consent through the last subject visit.

9.3. Definition of an Adverse Event

An adverse event is any untoward medical occurrence in a clinical investigation associated with the use of an investigational product in human subjects. The event need not necessarily have a suspected causal relationship with the treatment or usage.

Examples of adverse events include but are not limited to:

- Clinically significant symptoms and signs
- Changes in physical examination findings

• Hypersensitivity

Additionally, they may include the signs or symptoms resulting from:

- Product misuse
- Product dependency
- Extravasation
- Study related procedure (e.g., resistance training protocol)

9.4. Serious Adverse Events

A medical device adverse event is serious when both of the following criteria are fulfilled:

- The event involves patient/subject/consumer contact
- The event results in:
 - Death
 - Serious deterioration in state of health. This includes:
 - Life-threatening illness or injury
 - Permanent impairment of a body function
 - Permanent damage to a body structure
 - Requires medical or surgical intervention to prevent permanent impairment of a body function or permanent damage to a body structure
 - Requires inpatient hospitalization or prolongation of existing hospitalization

9.5. Severity Assessment

If required on the adverse event case report forms, the investigator will use the adjectives MILD, MODERATE, or SEVERE to describe the maximum intensity of the adverse event. For purposes of consistency, these intensity grades are defined as follows:

| MILD | Does not interfere with the subject's usual function. |
|----------|--|
| MODERATE | Interferes to some extent with the subject's usual function. |
| SEVERE | Interferes significantly with the subject's usual function. |

Note the distinction between the severity and the seriousness of an adverse event. A severe event is not necessarily a serious event. For example, a headache may be severe (interferes significantly with the subject's usual function) but would not be classified

serious unless it met one of the criteria for serious adverse events, listed above.

9.6. Causality Assessment

The investigator's assessment of causality must be provided for all adverse events (serious and non-serious). An investigator's causality assessment is the determination of whether there exists a reasonable possibility that the INP caused or contributed to an adverse event. If the investigator's final determination of causality is unknown and the investigator does not know whether or not INP caused the event, then the event will be handled as "related to INP" for reporting purposes. If the investigator's causality assessment is "unknown but not related to INP", this should be clearly documented on study records.

In addition, if the investigator determines a serious adverse event is associated with study procedures, the investigator must record this suspected causal relationship in the source documents and CRF, as appropriate, and report such an assessment in accordance with the serious adverse event reporting requirements, if applicable.

10. STATISTICAL METHODS

10.1. Sample Size Determination

The targeted sample size of 50 participants was determined by the Sponsor based on a meta-analysis involving 206,873 participants (Staiano et al., 2024). This analysis demonstrated that digital health interventions led to improvements in physical activity (+1,329 steps/day), reduced sedentary behavior (-7 hours/week), and increased vigorous exercise (+1 hour/week). Using these values, we conducted a power analysis, which identified an effect size difference of 0.8 between the control and experimental groups for average changes in habits like daily steps. This analysis confirmed that a sample size of 50 subjects would be sufficient.

https://trialsjournal.biomedcentral.com/articles/10.1186/s13063-015-0950-4

10.2. Demographics and Baseline Characteristics

Demographic information will include age, gender, height, weight, BMI, race, and ethnicity. Baseline characteristics, including health data, subjective questionnaires, and anthropometrics will be summarized by treatment.

10.3. Analyses

10.3.1 Primary Analysis

Descriptive statistics will be reported including mean, median, minimum and maximum values, standard deviation, and 95% confidence intervals of the mean. All outcome measure data will be reported as mean \pm standard deviation (SD). Relative and absolute changes between groups for all outcomes will be reported and analyzed for statistical significance using paired *t* tests. Additionally, effect sizes will be calculated as Cohen's d_g

for between-subjects analyses as the difference between group means divided by the pooled standard deviation times a correction factor [1]. Statistical significance will be set at p < 0.05 and all analyses will be performed using SPSS Version 28.0.

Cohen's
$$d_g = \frac{\left(X_{Group A} - X_{Group B}\right)}{SD_{pooled}} \times \left(1 - \frac{3}{4 \times (N1 + N2) - 9}\right)$$

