4. OUTCOMES MEASURE

- 4.1. Primary Outcomes these measures will be taken at week 0 (pre) and week 7 (post)
 - Healthspan, as assessed via a digital score within the application software.
 - **Biological Age**, as assessed via an algorithm sourced within the application.
 - Lifestyle Risk Factors, as assessed via questionnaires within the application.
 - Energy and Vitality, as assessed via questionnaires within the application.
 - Strength and Endurance, as assessed by performance measures including a timed mile walk/run, push-ups to exhaustion, and chair get-ups to exhaustion.
 - Body Composition, as assessed via a previously validated digital scale.
 - Blood Pressure, as assessed via an electronic blood pressure cuff.
 - Lifestyle Habits, as assessed by specific interfaces within the application and guided by an AI "coach."
 - **Daily Steps**, as collected via the Apple Health or Google Fit application on the subject's pre-existing personal device.

4.2. Secondary Outcomes – these measures will be taken at week 0 (pre) and week 7 (post)

- **Depression**, as assessed by the previously validated PHQ-9 subjective questionnaire.
- Quality of Life, as assessed by the previously validated SF-36 subjective questionnaire.

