5. INVESTIGATIONAL PLAN

5.1. Overall Study Design and Plan

This is a non-blinded randomized controlled pilot trial conducted over up to 8 weeks. Week 0 will involve baseline measurements and enrollment, Weeks 1-6 constitute the intervention, and Week 7 to 8 is reserved for post-testing. The study will enroll up to 200 participants, with a minimum of 50 participants who meet the inclusion criteria, and a minimum target of 20 participants completing the study in each group (experimental and control).

Participants will be recruited from across the United States using a decentralized electronic database. The study will include individuals aged 21-60 with a BMI \geq 25 (overweight) and \leq 35. Additionally, qualified subjects must have current daily activity records that show an average daily step count under 5,000. Participants must also be free of disease and must own either a personal smartphone device with the Apple Health or Google Fit application. Finally, participants must be willing to keep their device with them at all times to ensure accurate activity tracking.

Following baseline testing and enrollment in the study, participants will be randomly assigned to either the control (CON) or experimental (PRO) group. The control group will receive subject-facing materials depicting current general activity recommendations as published by the American Heart Association (AHA) and current dietary guidelines provided by the United States Department of Agriculture (USDA). The experimental group will be enrolled in the Prime Health Technologies software (Pro2col), which provides a digital diagnostic score to calculate healthspan and biological age, along with AI and group community-based coaching dynamics. Subjects will be assigned a 6 week progressive protocol targeting improvements in daily activity levels, nutritional awareness, and overall lifestyle risk factors. Both groups will then be monitored by study staff throughout the duration of the intervention period with post-testing taking place following the last week of the experiment.

Due to the remote nature of subject recruitment, no in-person facility visits are required for participants.

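### The only named test is a paired t test applied to changes between two independent randomised arms, so the plan has no proper test of app versus control

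*Combined protocol and SAP*

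**What the plan says.** Section 10.3.1 has one sentence on significance testing, and it covers every outcome: "Relative and absolute changes between groups for all outcomes will be reported and analyzed for statistical significance using paired *t* tests". The threshold follows: "Statistical significance will be set at p < 0.05". The same section plans an effect size "for between-subjects analyses as the difference between group means divided by the pooled standard deviation times a correction factor", with separate group sizes N1 and N2 in the formula.

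Section 5.1 gives the design: "participants will be randomly assigned to either the control (CON) or experimental (PRO) group". It sets a floor of 20 completers per arm and allows total enrolment from 50 up to 200. Section 4 has the outcomes measured before and after the intervention. Section 10.1 bases the sample size of 50 on "an effect size difference of 0.8 between the control and experimental groups for average changes in habits like daily steps".

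No independent-samples test, ANCOVA, mixed model or other between-arm test appears anywhere in the document.

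**The concern.** A paired t test needs a defined link between the two values in each pair. The only such link here is a subject's own pre and post values. The sentence nevertheless applies the test to changes between groups, and it can be read in two ways.

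- **Reading A: pre versus post within each arm.** This is a valid test of change over time, but it does not compare the arms. Several things can move both arms without any app effect: practice on the push-up, chair and mile tests, regression to the mean after selecting people with under 5,000 daily steps (section 5.2.1), and unblinded participation (section 6.4). A result that is significant in the app arm and not in control could then be reported as efficacy.
- **Reading B: control subjects paired with app subjects.** No pairing rule exists, and the test needs equal numbers of completers, which a floor of 20 per arm does not secure. The p-value would depend on who is paired with whom.

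What is at stake is the comparison for which the control arm was recruited, for every efficacy outcome.

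**Working it through.** **Inputs.** From the documents: effect 0.8 and N = 50 (section 10.1), alpha 0.05 (section 10.3.1), at least 20 completers per arm and enrolment up to 200 (section 5.1). Assumed because not stated: two-sided test, 80% power, 1:1 allocation.

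**1. Reproduce the sample size.** For two independent means under the normal approximation, n per arm = 2(z₀.₉₇₅ + z₀.₈₀)²/d² = 2(1.960 + 0.842)²/0.8² = 24.5, so 25 per arm and 50 in total. This is the stated figure. The exact t calculation gives 25.5, so 26 per arm and 52 in total. A paired test with a mean difference of 0.8 SD of the within-pair differences needs 14.3, so 15 pairs. The stated N fits an independent comparison. Exact power of that comparison at d = 0.8 is 79% with 25 per arm and 69% with 20.

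**2. Reading A.** Let both arms have the same true change δ, in units of the SD of change, with no app effect. Within-arm power p is the noncentral-t power with noncentrality δ√n and n − 1 degrees of freedom. The arms are independent, so the chance that only the app arm is significant is p(1 − p). The values of δ are illustrative.

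| n per arm | δ | App arm significant (p) | App arm only, p(1 − p) |
|---|---|---|---|
| 20 | 0.2 | 14% | 12% |
| 20 | 0.3 | 25% | 19% |
| 20 | 0.5 | 56% | 25% |
| 25 | 0.2 | 16% | 13% |
| 25 | 0.3 | 30% | 21% |
| 25 | 0.5 | 67% | 22% |
| 100 | 0.2 | 51% | 25% |
| 100 | 0.3 | 84% | 13% |
| 100 | 0.5 | 99.9% | 0.1% |

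At 25 per arm and δ = 0.3, for example, p = 0.302 and 0.302 × 0.698 = 0.211. The 100-per-arm rows correspond to the enrolment ceiling of 200.

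**3. Reading B.** Differencing two unrelated subjects multiplies the SD by √2, so the standardised difference is 0.8/√2 = 0.566.

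- Power is 77% with 25 pairs and 67% with 20 pairs, about 2 points below the independent test.
- Simulated type I error over 20,000 normal trials is about 5%.
- For 40 simulated data sets of 25 per arm, each fixed at p = 0.05 in the independent test, 1,000 random pairings each gave p from about 0.02 to 0.10 (middle 95%).

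**4. Gain from ANCOVA.** If pre and post variances are equal, the ANCOVA error variance is (1 + r)/2 times that of the change score, where r is the pre-post correlation (assumed). At d = 0.8 on the change scale, power with 25 per arm is 89% (r = 0.5) or 85% (r = 0.7), against 79% for the change score. With 20 per arm it is 81% or 76%, against 69%.

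**The case against.** The strongest reply is that this is a drafting slip with a recognisable intent. Section 10.1 is powered on a between-group difference in changes, and section 10.3.1 defines a between-subjects effect size with a pooled SD. If that effect size is computed on changes, which the plan does not say, a reader could recover Student's t as the uncorrected d times √(N1·N2/(N1 + N2)). This helps the reader of a report. It does not prespecify a test, and it leaves the choice to be made after the data are seen in an unblinded trial.

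Other points stand in part:

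- Reading B is unlikely in practice, and a test done that way would hold its error rate. Its fault is dependence on the pairing, not bias.
- The harm under reading A needs a shared change, whose size the documents do not give, and someone who takes a within-arm result as an app effect. The plan states no such decision rule. A significant pre-post change in the app arm is, in itself, a correct finding about change over time.
- The figures at 20 and 25 per arm describe the low end of enrolment. At 100 per arm the pattern differs, as the table shows, but does not disappear.
- The ANCOVA gain needs equal pre and post variances. Baseline steps are restricted at entry, so their SD may be smaller. If the ratio of pre to post SD equals r, the gain vanishes and power with 25 per arm stays at 79%.
- The trial is an exploratory pilot (sections 3.1 and 5.1), which limits the consequence. It still randomises to a control, cites a power analysis and declares significance.

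**Conclusion.** The concern holds, and the sentence must be corrected. The named test does not fit two independent arms, and it disagrees with the plan's own effect size and sample size. On the more plausible pre/post reading, the app-versus-control comparison has no test. With no app effect and a shared change of 0.2 to 0.5 SD, the app arm alone would be significant in about 12% to 25% of trials with 20 or 25 per arm. On the other reading the test is valid but its p-value is not reproducible. These sizes rest on the assumed shared change, two-sided testing and equal arms. The mismatch between test and design rests on none of them. The sample size of 50 is not itself called into question: it is consistent with an independent comparison at an assumed 80% power.

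**What to change.** In section 10.3.1, replace the paired t tests with a named between-arm test for each outcome, and fix the choice before the data are analysed.

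- **Minimum:** an independent-samples (Welch) t test on absolute change.
- **Preferred:** ANCOVA with the post-test value as response, arm as factor and the baseline value as covariate. Baseline is already collected.
- State which of the two is primary. Report the between-arm difference with its 95% confidence interval and two-sided p-value.
- Say what is done with relative change, which the current sentence also tests. Reporting it descriptively would be enough.
- Keep within-arm pre/post results descriptive, without p-values.

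The cost is a change of wording, handled as an amendment with sponsor agreement and written IRB/IEC approval under section 12.1. No new data or additional subjects are needed, and SPSS runs either test.
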